7.2.4 SPECIMEN SHIPMENT

The laboratory work will be done at the Moffitt Cancer Center. The samples will be analyzed for correlative studies. Submit materials for translational research as detailed in the lab manual.

7.3 STUDY SCHEDULE

7.3.1 SCREENING

Screening Visit (Day -28 to -0)

Before performing any procedures or assessments, the nature of the study and the potential risks associated with the trial will be explained to all subject candidates and written informed consent will be obtained. Once informed consent has been obtained (within 8 weeks of first dose of study drug), the following procedures and evaluations will be performed:

- Verify inclusion/exclusion criteria
- Measurable disease by RECIST 1.1 using computerized tomography/magnetic resonance imaging (CT/MRI) or photographs of pertinent sites involved with disease.
- Obtain vital signs (systolic and diastolic BP, HR, RR, and body temperature) and weight. BP, HR, and RR will be obtained after subjects have been resting for 5 minutes.

- Perform a comprehensive physical examination (including a neurological evaluation).
- Collect blood samples for laboratory testing and pregnancy test if indicated.
- Collect urine or serum sample for β -hCG pregnancy testing from all women of childbearing potential.
- Record all prior and concomitant medication use (prescription and nonprescription medications as well as transfusions).
- Plan for obtaining tumor tissue.
- Collect research blood sample (may be collected on Cycle 1 Day 1 prior to therapy)

The screening form must be completed for all subjects screened, providing reasons for screen failure when applicable.

7.3.2 ENROLLMENT/BASELINE

Enrollment/Baseline: Cycle 1 Day 1 (cycle = 3 weeks)

The baseline assessment can be performed on Cycle 1 Day 1 (C1D1), prior to treatment.

Clinical and laboratory assessments are valid if obtained within 72 hours of baseline assessment.

- Obtain informed consent or verify previously obtained during screening signed informed consent form.
- Verify inclusion and exclusion criteria.
- Obtain laboratory tests.
- Confirm negative urine/serum pregnancy test.
- Obtain demographic information, medical history, medication and social history.
- Evaluate ECOG performance status.
- Obtain vital signs.
- Record all concomitant medication use.
- Perform a comprehensive physical examination.
- Establish new baseline tumor assessments (selection of target and non-target lesions) based upon scans taken (CT and/or MRI) or lesions photographed unless performed within 4 weeks.
- Educate about potential AEs and SAEs. Encourage early recognition and reporting.
- Obtain tumor tissue (should be done prior to initiation of therapy).
- Collect research blood sample (only if not collected during screening)

7.3.3 TREATMENT VISITS

On Treatment Visits

Study participants will be seen every 3 weeks before each cycle (Cycle 1 Day 1, Cycle 2 Day 1, etc).

In each scheduled visit we will:

- Obtain vital signs.
- Record all concomitant medication use.
- Perform a comprehensive physical examination.
- Obtain laboratory tests.
- Assess for AEs and SAEs.
- Assess compliance with the medication.
- Assess survival.
- Collect research blood sample (Cycles 3, 6, 9 and 12 only)
- Cemiplimab administration

Diagnostic imaging

Diagnostic imaging of affected and suspected sites (CT, MRI and/or photographs) will be done at Day 1 of cycles 3, 6, 9, 12, and 15 (or between Day 15-21 of the prior cycle) in all patients. Diagnostic imaging will continue to be done every 2 months thereafter or as clinically indicated otherwise.

7.3.4 END OF TREATMENT VISIT

An End of Treatment (EOT) visit will be performed for all subjects. At the end of treatment (30 days after last Cemiplimab-rwlc dose) the following data will be collected:

- Obtain vital signs.
- Record all concomitant medication use.
- Perform a comprehensive physical examination.
- Obtain laboratory tests.
- Assess for AEs and SAEs.
- Assess compliance with the medication.
- Assess survival.
- Optional fresh tumor biopsy (in order to accommodate scheduling, this biopsy may occur up to an additional 30 days beyond the EOT visit).
- Diagnostic imaging of affected and suspected sites (CT, MRI and/or photographs), if not performed within the last 8 weeks.
- Collect research blood sample

7.3.5 FOLLOW-UP

To assess for late toxicities, at 6 months and 12 months after EOT patients will return for a physical exam and labs, unless the patient has enrolled in hospice care or is otherwise unwilling/unable to return to clinic.

For this protocol, all patients, including those who discontinue protocol therapy early, will be followed for response until progression and for survival for 2 years from the start of treatment. All patients must also be followed through completion of all protocol therapy. Patients removed from study for unacceptable adverse events will be followed until resolution or stabilization of the adverse event. Follow-up for survival will be performed every 90 days (\pm 2 weeks) from the end of treatment visit.

Research blood collection to be performed at the end of study (2 years after initiation of study treatment).

7.3.6 UNSCHEDULED VISIT

Unscheduled visits may be related but not limited to development of Cemiplimab-rwlc toxicities. In that

case the Grade of toxicity will be documented and the medication dose will be adjusted as per protocol. All unscheduled visit will be documented in the patients chart.

7.3.7 SCHEDULE OF EVENTS TABLE

Table 3. Schedule of events

Phase	Screen	Experimental phase																	EOT ^k	Follow-Up	
		1	2	3	4	5	6	7	8	9	10	11	12	13	14	15	16	17			
Cycle (21 days)	0																				
Day ^a	-28 to -0	1	1	1	1	1	1	1	1	1	1	1	1	1	1	1	1	1	30	Q3 months	
Assessments																					
Informed consent ^b	X ^c																				
Inclusion/exclusion	X ^c																				
Demographic data	X ^c																				
Medical history	X ^c																				
ECOG	X ^c																				
Vital signs ^d	X ^c	X ^c	X	X	X	X	X	X	X	X	X	X	X	X	X	X	X	X	X ^m		
Physical exam ^e	X ^c	X ^c	X	X	X	X	X	X	X	X	X	X	X	X	X	X	X	X	X ^m		
Laboratory tests ^f	X ^c	X ^c	X	X	X	X	X	X	X	X	X	X	X	X	X	X	X	X	X ^m		
Pregnancy test ^g	X ^c																				
Imaging studies (CT/MRI) ^h	X ^c			X			X			X			X			X			X ⁱ		
Mandatory research blood collection	X			X			X			X			X						X	X ⁿ	
Tumor collection	Mandatory: - Archival Optional: - Fresh Tissue																		Optional: - Fresh Tissue		
Cemiplimab Administration		X	X	X	X	X	X	X	X	X	X	X	X	X	X	X	X	X			
Concomitant meds ^j	X	X		X			X			X			X			X			X		
AEs/SAEs ^j		Throughout																X			
Survival		Throughout																X		X	

a: Efforts should be made to conduct study visits on the day scheduled (\pm 3 days). Clinical and laboratory assessments may be conducted anytime within 72 hours prior to the scheduled visit, unless otherwise specified in the Schedule of Visits and Procedures.

b: Informed consent may be taken up to 8 weeks prior to C1D1.

c: The baseline assessment can be performed on Cycle 1 Day (C1D1), prior to treatment. Clinical and laboratory assessments are valid if obtained within 72 hours of baseline assessment.

d: Assessments will include vital signs (resting BP, HR, RR, and body temperature and weight. BP, HR, and RR will be obtained after subjects have been resting for 5 minutes.

e: Comprehensive physical examination (including a neurological evaluation).

f: Laboratory tests include: CBC w/differential, CMP, ALT, AST, magnesium, amylase, lipase, TSH, and if clinically indicated INR.

g: Serum or urine, in women of childbearing potential only.

h: Baseline images to include CT/MRI of head /neck/ chest/abdomen/pelvis and other areas of known disease or clinical measurements and/or photographs of superficial tumors. On treatment imaging will include only areas of known disease plus any areas of newly suspected disease.

i: All concomitant prescription medications taken during study participation will be recorded on the case report forms (CRFs).

j: AEs/SAEs will be assessed during each visit clinically and based on laboratory data. Patients will be encouraged to report AEs/SAEs at the earliest recognition via the phone between the visits.

k: End of Treatment visit is to occur 30 days after the last dose of Cemiplimab-rwlc therapy ± 7 days. If the subject is unable or unwilling to return to clinic this visit can be conducted via a telephone call.

l: May be omitted if performed within the last 8 weeks.

m: Physical exam and labs required at 6 months and 12 months after EOT only to assess for late AEs, unless the patient has enrolled in hospice care or is otherwise unwilling/unable to return to clinic.

n: Research blood collection to be performed at the end of study (2 years after initiation of study treatment).

7.4 CONCOMITANT MEDICATIONS, TREATMENTS, AND PROCEDURES

All concomitant prescription medications taken during study participation will be recorded on the case report forms (CRFs).

All additional local therapies for metastatic lesions (including, but not limited to EBRT, surgery, embolization, ethanol injections, etc.) will be recorded on CRFs.

- Steroid: Treatment with oral/IV corticosteroids (>10mg daily prednisone equivalent) is not allowed for non-immunological toxicities. Treatment with oral/IV corticosteroids (>10mg daily prednisone equivalent) for immunological toxicities is permitted as detailed in the dose modification sections.
- Use of corticosteroids (\leq 10 mg daily prednisone equivalents) is allowed. Inhaled or topical steroids and adrenal replacement doses $>$ 10 mg daily prednisone equivalents are permitted in the absence of active autoimmune disease.
- Palliative radiation therapy is allowed to non-target lesions at the discretion of the treating physician. As concurrent radiotherapy and Cemiplimab-rwlc have not been formally evaluated, in cases where palliative radiotherapy is required for a tumor lesion, then Cemiplimab-rwlc should be withheld for at least 1 week before, during, and 1 week after radiation. Subjects should be closely monitored for any potential toxicity during and after receiving radiotherapy.
- Surgical resection of new and non-target cutaneous lesions that are $<$ 10mm is allowed at the discretion of the treating physician. Surgical resection of target lesions is only permissible if all previously identified target lesions are rendered operable. For guidance on the impact on response assessment refer to the composite response criteria found in Appendix 2.

7.5 JUSTIFICATION FOR SENSITIVE PROCEDURES

7.5.1 PRECAUTIONARY MEDICATIONS, TREATMENTS, AND PROCEDURES

Not Applicable.

7.6 PROHIBITED MEDICATIONS, TREATMENTS, AND PROCEDURES

- Steroid: Treatment with oral/IV corticosteroids (>10mg daily prednisone equivalent) is not allowed for non-immunological toxicities. Treatment with oral/IV corticosteroids (>10mg daily prednisone equivalent) for immunological toxicities is permitted as detailed in the dose modification sections.

7.7 PROPHYLACTIC MEDICATIONS, TREATMENTS, AND PROCEDURES

Not Applicable.

7.8 RESCUE MEDICATIONS, TREATMENTS, AND PROCEDURES

Immuno-oncology agents are associated with AEs that can differ in severity and duration than AEs caused by other therapeutic classes. Cemiplimab-rwlc is considered an immune-oncology agent in this protocol. Early recognition and management of AEs associated with immuno-oncology agents may mitigate severe toxicity. Management Algorithms have been developed to assist investigators in assessing and managing the following groups of AEs:

- Gastrointestinal
- Renal
- Pulmonary
- Hepatic
- Endocrinopathy
- Skin
- Neurological

The above algorithms can be found in [Appendix 1](#)

Hypersensitivity infusion reactions should be reported to the site principal investigator and Regeneron Pharmaceuticals, Inc. within 24 hours of the event regardless of grade. The following AE terms constitute hypersensitivity infusion reactions:

- Allergic reaction
- Anaphylaxis
- Cytokine release syndrome
- Serum sickness
- Infusion reactions
- Infusion-like reactions

Management of infusion reactions.

Infusion reaction treatment guidelines are summarized in Table 4 below. Institutional standards for infusion reactions may be followed if the treating physician deems them acceptable for this protocol.

Table 4. Management of infusion reaction

Grade 1 Mild reaction	Increase monitoring of vital signs as medically indicated until the patient is deemed medically stable in the opinion of the investigator	None
Grade 2 Requires infusion interruption but responds promptly to symptomatic treatment (i.e., antihistamines, NSAIDS, narcotics, IV fluids); prophylactic medications indicated for ≤ 24 hours	
Stop infusion and monitor symptoms.
 
Additional appropriate medical therapy may include but is not limited to:
 
• IV fluids• Antihistamines• NSAIDS• Acetaminophen• Narcotics 
Increase monitoring of vital signs as medically indicated until the patient is deemed medically stable in the opinion of the investigator.
 
If symptoms resolve within one hour of stopping drug infusion, the infusion may be restarted at 50% of the original infusion rate.
 
Otherwise, dosing will be held until symptoms resolve, and the patient should be premedicated for the next scheduled dose.
 
Patients who develop Grade 2 toxicity despite adequate premedication should be permanently discontinued from further trial treatment administration.
	Subject may be premedicated 1.5h (\pm 30 minutes) prior to infusion of cemiplimab with: 
• Diphenhydramine 50 mg PO (or equivalent dose of antihistamine)• Acetaminophen 500-1000 mg PO (or equivalent dose of antipyretic)

Grade 3 or 4 Grade 3: Prolonged (i.e., not rapidly responsive to symptomatic medications and/or brief interruption of infusion); recurrence of symptoms following initial improvement; hospitalization indicated for other clinical sequelae (e.g., renal impairment, pulmonary infiltrates) Grade 4: Life-threatening; pressor or ventilatory support indicated	
Stop infusion.
 
Additional appropriate medical therapy may include but is not limited to:
 
• IV fluids• Antihistamines• NSAIDS• Acetaminophen• Narcotics• Oxygen• Pressors• Corticosteroids• Epinephrine 
Increase monitoring of vital signs as medically indicated until the patient is deemed medically stable in the opinion of the investigator.
 
Hospitalization may be indicated.
 
Patient is permanently discontinued from further trial treatment administration.
	No subsequent dosing
---	--	----------------------

7.9 PARTICIPANT ACCESS TO STUDY AGENT AT STUDY CLOSURE

Cemiplimab-rwlc is an FDA approved drug for treatment of CSCC. Study participant may choose to continue Cemiplimab-rwlc as per standard of care if indicated upon study closure.

8 ASSESSMENT OF SAFETY

8.1 SPECIFICATION OF SAFETY PARAMETERS

Study participants will be monitored closely based on clinical, laboratory and imaging studies as outlined in study calendar (Table 3). Patients will be educated and encouraged to report any AEs and SAEs promptly. All AEs and SAEs will be graded according to CTCAE v5.0 and recorded in patient's charts and CRFs.

8.1.1 DEFINITION OF ADVERSE EVENTS (AE)

An adverse event (AE) is defined as any untoward medical occurrence, including an exacerbation of a pre-existing condition, in a patient in a clinical investigation who received a pharmaceutical product. The event does not necessarily have to have a causal relation with this treatment. Grade 1 toxicities and lab abnormalities not deemed clinically significant will not be collected.

8.1.2 DEFINITION OF SERIOUS ADVERSE EVENTS (SAE)

A serious adverse event (SAE) is defined as any AE that results in death, is immediately life-threatening, results in persistent or significant disability/incapacity, requires or prolongs patient hospitalization, is a congenital anomaly/birth defect, or is to be deemed serious for any other reason if it is an important medical event when based on appropriate medical judgement that may jeopardize the patient and may require medical or surgical intervention to prevent one of the other outcomes listed in the above definitions.

In addition, all reports of spontaneous abortion, abuse, and/or drug dependency shall be considered as SAEs for regulatory reporting purposes.

Patients may be hospitalized for administrative or social reasons during the study (e.g., days on which infusion takes place, long distance from home to site). These and other hospitalizations planned at the beginning of the study do not need to be reported as an SAE in case they have been reported at screening visit in the source data and have been performed as planned.

8.1.3 DEFINITION OF UNANTICIPATED PROBLEMS

Unanticipated adverse therapy effect, any serious adverse effect on health or safety, or any life-threatening problem or death caused by, or associated with, if that effect, problem, or death was not previously identified in nature, severity, or degree of incidence or any other unanticipated serious problem associated with the therapy that relates to the rights, safety, or welfare of subjects.

8.2 CLASSIFICATION OF AN ADVERSE EVENT

8.2.1 SEVERITY OF EVENT

All AEs will be graded using the CTCAE 5.0 criteria.

For AEs not included in the protocol-defined grading system, the following guidelines will be used to describe severity.

Mild – Events require minimal or no treatment and do not interfere with the participant's daily activities.

Moderate – Events result in a low level of inconvenience or concern with the therapeutic measures. Moderate events may cause some interference with functioning.

Severe – Events interrupt a participant's usual daily activity and may require systemic drug therapy or other treatment. Severe events are usually potentially life-threatening or incapacitating.

8.2.2 RELATIONSHIP TO STUDY AGENT

For all collected AEs, the clinician who examines and evaluates the participant will determine the AE's causality based on temporal relationship and his/her clinical judgment. The degree of certainty about causality will be graded using the categories below.

Related – The AE is known to occur with the study agent, there is a reasonable possibility that the study agent caused the AE, or there is a temporal relationship between the study agent and event. Reasonable possibility means that there is evidence to suggest a causal relationship between the study agent and the AE.

Not Related – There is not a reasonable possibility that the administration of the study agent caused the event, there is no temporal relationship between the study agent and event onset, or an alternate

etiology has been established.

8.2.3 EXPECTEDNESS

The PI will be responsible for determining whether an AE is expected or unexpected. An AE will be considered unexpected if the nature, severity, or frequency of the event is not consistent with the risk information previously described for the study agent.

8.3 TIME PERIOD AND FREQUENCY FOR EVENT ASSESSMENT AND FOLLOW-UP

The study participants will be monitored closely throughout the study for occurrence of AE or SAE. The patients will be educated regarding most common AEs and SAEs and will be encouraged to report promptly.

If AEs and SAEs occur, information to be collected includes event description, time of onset, clinician's assessment of severity, relationship to study product, and time of resolution/stabilization of event. All AEs occurring during the study will be documented appropriately, regardless of relationship. All AEs will be followed to adequate resolution.

Any medical condition that is present at the time that the participant is screened will be considered as baseline and not reported as an AE. However, if the study participant's condition deteriorates at any time during the study, it will be recorded as an AE. Unanticipated problems will be recorded in the data collection system throughout the study.

Events will be followed for outcome information until resolution or stabilization is achieved.

8.4 REPORTING PROCEDURES

8.4.1 ADVERSE EVENT REPORTING

All AEs occurring prior to initiation of Cemiplimab-rwlc therapy do not need to be reported.

All AEs occurring after first administration of Cemiplimab-rwlc therapy and 30 days after last administration of Cemiplimab-rwlc will be considered as on treatment. All AEs will be collected and graded according to CTCAE v5.0, with the exception of Grade 1 laboratory abnormalities which will not be collected. All Grade 2 and above toxicities will be collected and documented by the investigator, but only Grade 3 toxicities deemed possibly, probably or definitely related to the study treatment will be reported on the appropriate CRFs/SAE reporting forms. Only SAEs will be reported to the PI and Regeneron Pharmaceuticals, Inc. All AEs, including those persisting after end of study treatment must be followed up until they have resolved or have been sufficiently characterized or the principal investigator decides to not further pursue them.

Serious and non-serious AEs occurring later than 30 days after last administration of trial drugs will only be reported in case they are considered drug-related or trial (procedure) related.

Deaths (unless they are considered drug-related or trial related) will not be reported as SAE when

they occur later than 30 days after last administration of the trial.

Serious and non-serious AEs occurring after the subjects initiate subsequent treatment will only be collected if deemed related to cemiplimab-rwlc.

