7.2.2 OTHER ASSAYS OR PROCEDURES

Patients from the parent study will be eligible for participation on an optional basis in a tissue biomarker study and the blood collection for the biomarker correlative study.

In all study participants, submission of archived diagnostic formalin fixed paraffin embedded (FFPE) tumors obtained at any time prior to Cemiplimab-rwlc treatment is required. Additionally, tumor tissue will be obtained from the most accessible locations for a biopsy prior to initiation and at the end of Cemiplimab-rwlc therapy. These biopsies for only research purposes are OPTIONAL. Any metastatic cancer tissue obtained during the study (including but not limited to excisional, core biopsies, surgical specimens, etc.) will be subject to additional molecular studies in the future.

PROPOSED BIOMARKER EVALUATIONS

7.2.2.1 *Determination of the genomic landscape to determine tumor mutation burden*

The archived FFPE primary tumors (and subsequent metastatic tumors if available) will be analyzed by whole exome sequencing, and the comprehensive genomic landscape and tumor mutation burden will be assessed.

7.2.2.2 *Evaluation of the Tumor Immune Microenvironment*

Intact immune system is critical for tumor surveillance. Comprehensive evaluation of tumor immune microenvironment has not been fully characterized. An innovative methodology, multiplex immune-histochemical (mIHC) staining, allows the analysis of an array of markers from limited sample specimens. The evaluation of a complex cellular microenvironment is best accomplished using mIHC which enables simultaneous detection and measurement of multiple protein antigens on the same tissue section allowing accurate classification of cells as well as enumeration and quantification of

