7.2.3 SPECIMEN PREPARATION, HANDLING, AND STORAGE

SPECIMEN PREPARATION, HANDLING, AND STORAGE

Tissue specimens will be handled and stored according to the Laboratory Manual.

Tissue/Specimen Submission

Tumor tissue samples will be collected at pre- and post-treatment. The tumor tissue samples will be submitted to the Moffitt Tissue Core for banking and translational research.

Pre-treatment formalin-fixed paraffin-embedded (FFPE) archived tumor samples (MANDATORY)

Any archived tumor tissue (except FNA cell blocks) obtained before Cemiplimab-rwlc is allowed. An FFPE tumor block should be submitted with the submission form. A Pathology Report and one hematoxylin and eosin-stained slide documenting that the submitted block or unstained slides contain tumor should also be submitted with the tissue. The report and hematoxylin and eosin-stained slide must include the protocol number and patient's case number. The patient's name and/or other identifying information should be removed from the report. The surgical pathology numbers and information must NOT be removed from the report.

Pre- and post-treatment tumor biopsy (Day -21 to 0 before Cemiplimab-rwlc and at the End of Treatment visit; OPTIONAL)

The pre- and post-treatment tumor biopsy can be obtained from the primary site, lymph node metastasis, or other safely accessible site metastases as a punch biopsy or a core needle biopsy: one punch or core in formalin and the second punch or core in liquid nitrogen (or dry ice/ethanol slurry). The biopsy sample should be prepared: 1) as a formalin-fixed paraffin-embedded tumor block and 2) as a flash frozen sample in liquid nitrogen (or dry ice/ethanol slurry). The frozen specimens can be stored at -80°C (-70°C to -90°C).

CORRELATIVE WITH BLOOD

Blood samples must be submitted with the submission form documenting the date of collection of the sample; the protocol number, the patient's case number, time point of study, and method of storage (for example, stored at -80°C). The frozen specimens can be stored at -80°C (-70°C to -90°C).

The blood samples should be processed as detailed in the Laboratory Manual.

In brief,

1 x 10 ml Lavender EDTA tube and 1 x 8.5 ml LBgard tube of blood will be generated from each clinical event. The samples will be processed and shipped according to the Laboratory Manual.

Clinical events:

1. Pre-therapy (Anytime between Day -21 and Cycle 1 Day 1)
2. Cycle 3 Day 1 +/- 7 days
3. Cycle 6 Day 1 +/- 7 days

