8.4.2 SERIOUS ADVERSE EVENT REPORTING

All SAEs will be reported to the PI and Regeneron Pharmaceuticals, Inc. within 24 hours after identification and recorded in OnCore and Regeneron Pharmaceuticals, Inc. by the investigator. All deaths and immediately life-threatening events, whether related or unrelated to the study agent/procedure, will be recorded on the SAE Form and submitted to the PI and Regeneron Pharmaceuticals, Inc. within 24 hours of site awareness. All SAEs will be followed until satisfactory resolution or until the investigator deems the event to be chronic or the adherence to be stable.

The reporting to Regeneron Pharmaceuticals will be done by email, [contact].

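### Section 8.4.1 exempts every adverse event before the first dose from reporting, serious research-biopsy complications included, and conflicts with the SAE reporting sections

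*Combined protocol and SAP*

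**What the plan says.** **The exemption.** Section 8.4.1 opens with "All AEs occurring prior to initiation of Cemiplimab-rwlc therapy do not need to be reported". It names no exception by seriousness or cause. For events more than 30 days after the last dose, the same section takes a different line: serious and non-serious AEs "will only be reported in case they are considered drug-related or trial (procedure) related".

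**Research procedures before dosing.** Section 7.2.3 schedules a punch or core biopsy from Day -21 to 0 and again at End of Treatment. Section 7.2.2 says of these: "These biopsies for only research purposes are OPTIONAL". Section 7.2.3 also allows the first research blood sample at any time from Day -21 to Cycle 1 Day 1. Table 3 labels that collection mandatory.

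**Definitions.** Section 8.1.1 describes an AE as occurring in a trial patient who received a pharmaceutical product. Section 8.1.2 defines an SAE as an AE with a serious outcome.

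**SAE reporting.** Section 8.4.2 requires all SAEs to go to the PI and the drug supplier within 24 hours. It covers deaths and immediately life-threatening events "whether related or unrelated to the study agent/procedure". Section 8.6 sends SAEs from the protocol to the IRB and the sponsor, and section 16.2 requires information on all SAEs to be collected. None of the three gives a start date.

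**Documentation.** Section 8.3 adds: "All AEs occurring during the study will be documented appropriately, regardless of relationship".

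**The concern.** A biopsy taken only for research carries risk with no direct benefit to the patient, and the pre-treatment biopsy comes before any possible benefit from the drug. Harm from it belongs in the safety record that the Protocol Monitoring Committee and the IRB see. The only sentence in the protocol that expressly addresses the pre-dose period tells sites that such events need not be reported.

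The population makes the question practical. Patients have HIV or a hematologic malignancy, and section 5.1 admits platelets down to 50 x 10^9/L and ANC down to 1.0 x 10^9/L. Bleeding or infection after a biopsy is foreseeable, although section 7.2.3 limits sampling to safely accessible sites.

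The same procedure is also handled by two rules. A complication of the End of Treatment biopsy is covered by the procedure-related clause once more than 30 days have passed since the last dose. The same complication of the pre-treatment biopsy is exempt under 8.4.1.

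**Working it through.** No figure in the plan bears on this point, so the check sets the sections side by side for one case: a biopsy complication that needs hospitalization but is not life-threatening, with onset before the first dose.

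| Section | What it implies for this case |
|---|---|
| 8.4.1, pre-dose sentence | Need not be reported |
| 8.1.1 with 8.1.2 | On a literal reading neither an AE nor an SAE, because no product has been received |
| 8.4.2, all SAEs | Reportable within 24 hours, if it counts as an SAE |
| 8.4.2, deaths and life-threatening events | Does not apply to this case |
| 8.6 and 16.2 | Reported or collected, if it counts as an SAE |
| 8.3 | Documented, if it counts as an AE |
| 8.4.1, late-event clause | Would be reportable if the same event followed the End of Treatment biopsy more than 30 days after the last dose |

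**Step 1: is the procedure inside the exempt period?** Yes. The biopsy window is Day -21 to 0, and section 7.3.2 asks for tissue before therapy starts. The exemption turns on when the event begins, not when the biopsy is done. A complication that begins after the first infusion falls in the on-treatment period and is not exempt.

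**Step 2: do the SAE sections settle it?** Not reliably. They apply to SAEs, and the definitions leave open whether a pre-dose event is one. The definitions are not decisive either, since 8.4.1 itself speaks of AEs before therapy. The literal reading matters most for a patient whose biopsy complication prevents dosing altogether, because that patient never receives a product.

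**Step 3: does another route catch it?** Only weakly. Section 8.2.2 grades causality against the study agent, and 8.3 records relationship to study product. Neither provides for relationship to a procedure. The unanticipated-problem definition in 8.1.3 is framed around the therapy, and 8.4.3 leaves IRB reporting to the PI's discretion. The AE/SAE row of Table 3 shows no screening entry, but the table's layout is partly broken in the text available, so nothing rests on it.

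**Step 4: is the late-event contrast real?** Largely. The End of Treatment visit is 30 days after the last dose (plus or minus 7 days), and section 7.3.4 lets the biopsy slip by up to 30 further days. Most of those biopsies, or their complications, would therefore fall after day 30, where procedure-related events are kept.

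**Illustration of scale (assumed rates only).** The documents give neither a complication risk nor a biopsy uptake. If the risk of a serious complication is r per biopsy and n patients accept, the chance of at least one is 1 - (1 - r)^n:

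- All 27 accept: 1 - 0.99^27 = 0.238 at r = 1%; 1 - 0.95^27 = 0.750 at r = 5%.
- 14 accept: 1 - 0.99^14 = 0.131; 1 - 0.95^14 = 0.512.
- 9 accept: 1 - 0.99^9 = 0.086; 1 - 0.95^9 = 0.370.

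The first line is the ceiling on uptake among the 27 planned patients. All three lines count serious complications of any kind and onset, so they overstate the number that would be both exempt under 8.4.1 and not expressly named in 8.4.2.

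**The case against.** The strongest reply is that 8.4.1 is the general AE section, while 8.4.2, 8.6 and 16.2 are the specific SAE sections. All three speak of SAEs without a start date. A site could reasonably treat them as governing and report a serious biopsy complication. For deaths and immediately life-threatening events, 8.4.2 is explicit whatever the relation to the procedure. This stands. A reader might infer that serious complications of the pre-treatment biopsy will not be reported. The documents do not support that: they give conflicting instructions, and the outcome depends on which one a site follows.

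A second reply concerns 8.3. It asks that AEs be documented, whereas 8.4.1 waives reporting, and 8.4.1 itself separates the two for Grade 2 and higher toxicities. This also stands. The tension with 8.3 is weak, and it does not follow that pre-dose harm would be missing from source records.

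A third reply is that the biopsy is optional and taken from accessible sites, so events should be few. That is fair, and it is why the illustrative probabilities should carry no weight in the decision.

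These replies do not remove the conflict. The one sentence written for the pre-dose period contains an unqualified exemption, the AE definition supports it, and nothing states which section prevails.

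**Conclusion.** The inconsistency is real and worth correcting. Section 8.4.1, read with 8.1.1 and 8.1.2, exempts serious complications of the research biopsy or research blood draw before the first dose. Sections 8.4.2, 8.6 and 16.2 would include them. The exemption also departs from 8.4.1's own treatment of late procedure-related events. The exposed case is narrow: a serious, non-life-threatening complication of a research procedure with onset before dosing. Such an event could go unreported; the documents do not establish that it would.

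Its frequency cannot be derived from the documents. The 24% to 75% range is only an illustrative upper bound, resting on an assumed 1% to 5% risk and on all 27 patients accepting an optional biopsy. The conclusion rests on the wording alone. The response-rate analysis, the sample size of 27, the stated 83.8% power and the 0.0986 significance level are untouched.

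**What to change.** 1. **Section 8.4.1.** Reword the pre-dose sentence along these lines: AEs before the first dose need not be reported, except that from consent onward any SAE related to a study-specific procedure (research biopsy or research blood draw) is reported under 8.4.2.
2. **Section 8.1.1.** Extend the AE definition to consented participants undergoing a study procedure, so that the event can qualify as an SAE under 8.1.2. Without this, the change to 8.4.1 may have nothing to act on.
3. **Consistency.** State the same start point in 8.4.2, 8.6 and 16.2, and add relationship to study procedure to the causality assessment in 8.2.2 and the data items in 8.3.

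The exception can be limited to serious events. After dosing, 8.4.1 sends only treatment-related Grade 3 toxicities to the reporting forms, so making minor blood-draw events reportable before dosing would create a new imbalance.

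The cost is a few lines in an IRB-reviewed amendment, one causality category, and a very small number of extra reports. No efficacy analysis changes.
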